Appendix H Procedures at HVTN CRS for Part A

Visit	01 ¹	02 ²	03	04	05	06	07	08	09	Post
Day:		D0	D3	D6	D28	D56	D112	D116	D168	
Week:		W0	W0	W0	W4	W8	W16	W16	W24	
Procedure	Scr	Inf								
Study procedures										
Signed screening consent (if used)	X	—	—	—	—	—	—	—	—	—
Assessment of understanding	X	—	—	—	—	—	—	—	—	—
Signed protocol consent	X	—	—	—	—	—	—	—	—	—
Medical history	X	—	—	—	—	—	—	—	—	—
Complete physical exam	X	—	—	—	—	—	—		X	—
Confirm eligibility, obtain demographics, randomize	X	—	—	—	—	—	—	—	—	—
Infusion										
Solicited AE assessment ³	—	X	—	—	—	—	—	—	—	—
Abbreviated physical exam	—	X	X	X	X	X	X	—	—	—
Risk reduction counseling ⁴	X	X	—	—	X	X	X		X	—
Contraception status assessment ⁵	X	X	—	—	X	X	X		X	—
Social impact assessment	—	X	—	—	X	X	X		X	—
Behavioral risk assessment questionnaire ⁶	X	—	—	—	—	—	—		X	—
Social impact assessment questionnaire	—	—	—	—	—	X	—		X	—
Acceptability questionnaire	—	X	—	—	—	—	—		—	—
Outside testing questionnaire	—	—	—	—	—	—	—		X	
Concomitant medications	X	X	X	X	X	X	X		X	—
Intercurrent illness/Unsolicited AE assessment	—	X	X	X	X	X	X		X	—
HIV infection assessment ⁷	X	—	—	—	—	—	X		X	—
Confirm HIV test results provided to participant	—	X	—	—	—	—	—		X	X
Specimen collection⁸	X	X	X	X	X	X	X		X	—

Greyed-out column does not apply to Part A.

Footnotes for Appendix H

- ¹ Screening may occur over the course of several contacts/visits up to and including day 0 prior to study product administration.
- ² Specimens collected at Day 0 may be obtained within the 14 days prior to study product administration, except for a pregnancy test, which must be performed on urine or blood specimens within 48 hours prior to study product administration with negative results received prior to study product administration.
- ³ Solicited AE assessments are performed daily for at least 3 full days following study product administration. CRS staff will review and reconcile the diary with the participant and then report Solicited AEs. Participant diary reconciliation may happen as the data is available (see the HVTN 140/HPTN 101 SSP).
- ⁴ Includes transmission risk reduction counseling for HIV-infected participants.
- ⁵ Contraception status assessment is required only for participants who were assigned female sex at birth and who are capable of becoming pregnant.
- ⁶ Not applicable to HIV-infected participants.
- ⁷ Includes pretest counseling and HIV testing. A subsequent follow-up contact is conducted to provide post-test counseling and to report results to participant. Not applicable for participants diagnosed with HIV infection.
- ⁸ For specimen collection requirements, see [Appendix F](#).

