6.4.5 Analysis of neutralization activity and correlation with serum concentrations

6.4.5.1 Primary analyses of neutralization magnitude-breadth curves

To address Primary objective 3, at each specified timepoint, the area-under-the-magnitude-breadth curve (AUC-MB) to a global panel of pseudoviruses (57) will be computed for each participant in the PP cohort with evaluable neutralization ID₅₀ or ID₈₀ data, as described in (58). Magnitude–Breadth (M-B) curves maybe employed to display individual- and group-level response breadth as a function of magnitude. Response breadth is defined as the percentage of viruses in the panel with neutralization titer above certain thresholds. Two choices are to compare the M-B curves among arms, as follows: a non-parametric Wilcoxon rank sum test on the subject-specific area-under-the M-B curve (AUC M-B) or a Kolmogorov-Smirnov type test on the 2 group-average M-B curves. Simulations can be used to obtain 2-sided p-values for the latter test. Second, a weighted-average score-like variable may be constructed to account for the correlations between virus isolates as an integrated magnitude of responses to multiple isolates. Similar group comparison methods described in the first approach may be adopted. Details of either approach will be described in the SAP.

6.4.5.2 Secondary analyses of correlations between serum concentrations and serum neutralization levels

To address Secondary objective 1, pharmacodynamics (PD) models based on either linear or non-linear mixed effects models will be performed to characterize the correlation between serum concentration (observed or popPK model-predicted) and serum neutralization against each virus or the AUC-MB of serum neutralization against the panel. Data from all enrolled participants will be analyzed regardless of how many administrations and how much mAb dose they received (MITT analysis). Similar to the popPK analysis, data from specimens collected outside of the visit window may be included in the PK/PD analyses that account for the actual specimen collection time, and the actual time and dose amount of each product administration. Since the exact date of HIV infection is unknown, any serum level data from blood draws 4 weeks prior to an infected participant's last seronegative sample and thereafter may be excluded. All data from HIV-infected participants who have no seronegative samples postenrollment may be excluded from the analysis.

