Appendix F Laboratory procedures for Part A

Procedure	Ship to ¹	Assay location ²	Tube Type ⁴	Tube size (vol. capacity) ⁴	Visit:								
					1	2	3	4	5	6	7	8	9
					Screening visit ³	D0	D3	D6	D28	D56	D112	D116	D168
					W0				W4	W8	W16		W24
Study Product Administration													
BLOOD COLLECTION													
Screening/Diagnostic													
Screening HIV test	Local lab	Local lab	EDTA	5mL	5	—	—	—	—	—	—	—	—
HBsAg/anti-HCV	Local lab	Local lab	SST	5mL	5	—	—	—	—	—	—	—	—
Syphilis ⁹	Local lab	Local lab	SST	5mL	5	—	—	—	—	—	—	—	—
HIV diagnostics ⁷	UW-VSL / HSML-NICD	UW-VSL / HSML-NICD	EDTA	10mL	—	—	—	—	—	—	—	—	10
Safety labs ¹⁰													
CBC/ Differential	Local lab	Local lab	EDTA	5mL	5	5	—	—	—	5	—		5
Chemistry Panel ⁵	Local lab	Local lab	SST	5mL	5	5	—	—	—	5	—		5
Drug concentrations/detection													
PGDM1400LS concentration	CSR	HVTN Labs	SST	8.5mL	—	y	y	y	y	y	y		y
Humoral assays													
HIV-1 neutralizing Ab	CSR	HVTN Labs	SST	8.5mL	—	y	y	y	y	y	y		y
Non-neutralizing antiviral assays	CSR	HVTN Labs	SST	8.5mL	—	y	y	y	y	y	y		y
Anti-Drug Antibody (ADA)													
ADA detection assays (screening, confirmatory, titration)	CSR	HVTN Labs	SST	8.5mL	—	y	—	—	—	—	—		y
ADA functional assay	CSR	HVTN Labs	SST	8.5mL	—	y	—	—	—	—	—		y
Ab Reaction ¹¹													
Tryptase / C3 and C4 Complement / Cytokines	CSR	ARUP	SST	8.5mL	—	See footnote 12	—	—	See footnote 12			See footnote 12	
ADA detection assays (screening, confirmatory, titration)	CSR	HVTN Labs	SST	8.5mL	—	See footnote y	—	—	—	—	—		—
ADA functional assay	CSR	HVTN Labs	SST	8.5mL	—	See footnote y	—	—	—	—	—		—
STORAGE													
Serum	CSR	—	SST	8.5mL	—	76.5 ¹⁴	42.5	42.5	42.5	42.5	42.5		42.5
Visit total					25	86.5	42.5	42.5	42.5	52.5	42.5		62.5
56-Day total ¹³					25	112	154.0	197	239	292	95		105
URINE COLLECTION ¹⁰													
Urine dipstick ⁸	Local lab	Local lab				x	—	—	—	x	—		x
Pregnancy test ⁶	Local lab	Local lab				x	x ¹⁵	—	—	—	—		x

Footnotes for Appendix F

Greyed-out column does not apply to Part A.

¹CSR = central specimen repository; UW-VSL = University of Washington Virology Specialty Laboratory (Seattle, Washington, USA); HSML-NICD = HIV Sero-Molecular Laboratory-National Institute for Communicable Diseases (Johannesburg, South Africa)

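### Part A: Appendix H schedules an HIV test at Day 112, but Appendix F draws no HIV blood until Day 168; the two tables must be reconciled

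*Protocol*

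**What the plan says.** Appendix H (Part A procedures) marks the HIV infection assessment at screening, Visit 7 (D112) and Visit 9 (D168). Footnote 7 defines it: "Includes pretest counseling and HIV testing. A subsequent follow-up contact is conducted to provide post-test counseling and to report results to participant". Section 9.4 describes the assessment at follow-up visits in the same way. A companion row, the check that HIV results have reached the participant, is marked at D0, D168 and after the last visit. Sections 9.3 and 9.4 explain that this check concerns the result from the previous visit.

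Footnote 8 of Appendix H passes the reader on: "For specimen collection requirements, see" Appendix F. There the row "HIV diagnostics" has a dash at every visit, D112 included, until 10 mL at Visit 9 (D168). The printed visit totals are "25 86.5 42.5 42.5 42.5 52.5 42.5 62.5" mL and the 56-day totals "25 112 154.0 197 239 292 95 105" mL, for screening, D0, D3, D6, D28, D56, D112 and D168. The y-footnote of Appendix F lists the uses of the stored serum, and HIV diagnosis is not among them.

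Section 6.4.5.2, the secondary PK/PD analysis, ties the handling of infected participants to their seronegative samples. Where one exists, serum data from four weeks before the last such sample onward may be dropped. Where none exists: "All data from HIV-infected participants who have no seronegative samples postenrollment may be excluded from the analysis".

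**The concern.** Each table is coherent by itself. In Appendix H, each of the three HIV tests is followed by a mark for confirming results, so the D112 mark does not look like a stray entry. In Appendix F, the dash at D112 agrees with the printed volumes. A site using both would counsel a participant for an HIV test at D112 and find no tube to draw.

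The difference decides whether the 15 Part A participants, all dosed with an anti-HIV antibody, have a scheduled HIV test between screening and D168. Section 9.5 warns that such an antibody could in theory make infection harder to detect, so the test days should be unambiguous. The test days also matter to the analysis, because the exclusion rule in Section 6.4.5.2 depends on whether a postenrollment seronegative sample exists. The postinfection exclusions in Section 6.4.4.1 (concentrations and PK) and Section 6.4.6 (ADA and functional assays) need infection to be placed in time.

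**Working it through.** **1. Reproduce the Appendix F totals.** Sum the rows by visit, and sum visits over a 56-day look-back that includes the visit exactly 56 days earlier.

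| Visit | Components (mL) | Visit total | 56-day total |
|---|---|---|---|
| Screening | 5 + 5 + 5 + 5 + 5 | 25 | 25 |
| D0 | 5 + 5 + 76.5 | 86.5 | 111.5 (printed 112) |
| D3 | 42.5 | 42.5 | 154.0 |
| D6 | 42.5 | 42.5 | 196.5 (printed 197) |
| D28 | 42.5 | 42.5 | 239 |
| D56 | 5 + 5 + 42.5 | 52.5 | 291.5 (printed 292) |
| D112 | 42.5 | 42.5 | 52.5 + 42.5 = 95 |
| D168 | 10 + 5 + 5 + 42.5 | 62.5 | 42.5 + 62.5 = 105 |

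All printed totals are reproduced after rounding, with no HIV tube at D112. The dash is therefore not a fault of text extraction. In Part B, the D112 total in Appendix G is 71 = 51 + 5 + 5 + 10, so the tube is included there.

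**2. Infection detectable at D112.** Under Appendix F the next HIV draw is at D168.
- Target days: 168 − 112 = 56 days (8 weeks).
- Allowable windows of ±7 days (Appendix L): shortest (168 − 7) − (112 + 7) = 42 days; longest (168 + 7) − (112 − 7) = 70 days. The range is 6 to 10 weeks.
- A D112 test would itself be positive, so this participant has no postenrollment seronegative sample under either appendix. The D112 tube saves time here, not data.

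**3. Infection after D112.** Both appendices detect it at D168, so there is no delay. The difference lies in the data kept for the PK/PD analysis.
- Appendix F: the only scheduled postenrollment HIV draw is the positive one. All 7 sampling visits (D0, D3, D6, D28, D56, D112, D168) may be excluded.
- Appendix H: a negative D112 sample puts the cutoff at 112 − 28 = D84 (D77 to D91 across the window). D0, D3, D6, D28 and D56 are kept, which is 5 of 7.

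**4. Dating of infection.** Screening may be up to 56 days before enrollment. Without a D112 test, the interval between scheduled tests is up to 56 + 168 = 224 days at target (231 with the window). With one, the longest interval at target is 56 + 112 = 168 days.

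**5. How often case 3 might arise.** The documents give no HIV incidence. Assume 0.5 to 3 per 100 person-years.
- Time at risk from D112 to D168: 15 × 56 / 365.25 = 2.30 person-years.
- Expected infections: 2.30 × 0.005 = 0.012 to 2.30 × 0.03 = 0.069.

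**6. Blood volume if the D112 tube were added.** Visit 7: 42.5 + 10 = 52.5 mL. 56-day totals: D112, 52.5 + 52.5 = 105 mL; D168, 52.5 + 62.5 = 115 mL. The limit in Section 10.2 is 500 mL.

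**The case against.** The best defence is that this is a clerical mismatch with little reach. Appendix H defers to Appendix F for specimens, so sites have a governing table. Enrollment requires low HIV risk. Section 9.5 refers to a protocol-specific testing algorithm, and Section 10.1 to site laboratory instructions and study-specific procedures; these documents are not available here and may settle the visit. Serum is stored at D112, and look-back testing, although not listed, cannot be ruled out. Complete loss of a participant's PK/PD data is therefore a worst case.

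Most of this stands as a limit on size. It does not remove the contradiction: deferring on specimens does not cancel a test that Appendix H itself schedules, and the Protocol's own list of serum uses does not fill the gap.

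A reader might infer two stronger claims, and the documents support neither. The first is that a late infection costs all of a participant's data. The rule is permissive and belongs to the secondary PK/PD analysis. Safety data from all enrolled participants are analyzed (Section 6.4). The primary concentration analysis may exclude samples only from after infection (Section 6.4.4.1), and the ADA and functional analyses exclude only postinfection results (Section 6.4.6). The second is that one infection suffers both data loss and late detection. Steps 2 and 3 of the working show that these fall on different infections.

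**Conclusion.** The contradiction is certain: for Part A, Appendix H schedules HIV testing at D112 and Appendix F provides no specimen for it. Its consequences are narrow. If Appendix F is followed, an infection detectable at D112 is found about 8 weeks later at target days, or 6 to 10 weeks across the windows. Separately, a participant infected after D112 may lose 7 of 7 sampling visits from the secondary PK/PD analysis, where a negative D112 test would have kept 5. The postinfection exclusions in the PK and ADA analyses also become harder to apply, because infection is bracketed less tightly.

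The expected number of infections from D112 to D168 is about 0.01 to 0.07. This rests on an assumed incidence of 0.5 to 3 per 100 person-years in 15 participants, with no unscheduled or early-termination test and no look-back testing of stored serum. No safety conclusion is put at risk by the exclusion rule. The point is small, but it is worth correcting because it fixes when participants are tested and costs almost nothing.

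**What to change.** Reconcile three Part A rows so that all refer to the same visits: HIV diagnostics in Appendix F, and HIV infection assessment and confirmation of HIV test results in Appendix H. Which schedule is intended is for the sponsor to state.

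- If D112 testing is confirmed, enter the 10 mL EDTA tube at Visit 7 in Appendix F and update the totals to 52.5 mL (Visit 7), with 56-day totals of about 105 mL (D112) and 115 mL (D168).
- If it is not, remove the D112 mark from Appendix H and review the D168 confirmation mark, which would then have no D112 result to confirm.

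In the same edit, correct footnote 7 of Appendix F, which refers to visit 15 although Part A ends at Visit 9.

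The cost is a table correction and, if D112 testing stands, at most 10 mL of blood and one HIV test per participant: 15 tests and 150 mL across Part A.

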Appendix I Procedures at HVTN CRS for Part B

	Visit	01 ¹	02 ²	03	04	05	06	07	08	09	10	11	Post
Day:		D0	D3	D6	D28	D56	D112	D116	D168	D224	D280		
Week:		W0	W0	W0	W4	W8	W16	W16	W24	W32	W40		
Procedure	Scr	Inf 1					Inf 2		Phone contact				
Study procedures													
Signed screening consent (if used)	X	—	—	—	—	—	—	—	—	—	—	—	—
Assessment of understanding	X	—	—	—	—	—	—	—	—	—	—	—	—
Signed protocol consent	X	—	—	—	—	—	—	—	—	—	—	—	—
Medical history	X	—	—	—	—	—	—	—	—	—	—	—	—
Complete physical exam	X	—	—	—	—	—	—	—	—	—	X	—	—
Confirm eligibility, obtain demographics, randomize	X	—	—	—	—	—	—	—	—	—	—	—	—
Infusion	—	X	—	—	—	—	X	—	—	—	—	—	—
Solicited AE assessment ³	—	X	X ³	X ³	—	—	X ³	X ³	X ³	—	—	—	—
Abbreviated physical exam	—	X	X	X	X	X	X	X	X	X	—	—	—
Risk reduction counseling ⁴	X	X	—	—	X	X	X	X	X	X	X	X	—
Contraception status assessment ⁵	X	X	—	—	X	X	X	X	X	X	X	X	—
Social impact assessment	—	X	—	—	X	X	X	X	X	X	X	X	—
Behavioral risk assessment questionnaire ⁶	X	—	—	—	—	—	—	—	—	—	X	—	—
Social impact assessment questionnaire	—	—	—	—	—	X	—	—	X	—	X	—	—
Acceptability questionnaire	—	X	—	—	—	—	X	—	—	—	—	—	—
Outside testing questionnaire	—	—	—	—	—	—	—	—	—	—	X	—	—
Concomitant medications	X	X	X	X	X	X	X	X	X	X	X	X	—
Intercurrent illness/Unsolicited AE assessment	—	X	X	X	X	X	X	X	X	X	X	X	—
HIV infection assessment ⁷	X	—	—	—	—	—	X	—	—	X	X	X	—
Confirm HIV test results provided to participant	—	X	—	—	—	—	—	—	—	X	—	X	X
Specimen collection⁸	X	X	X	X	X	X	X	X	X	X	X	X	—

Footnotes for Appendix I

¹ Screening may occur over the course of several contacts/visits up to and including day 0 prior to study product administration.

² Specimens collected at Day 0 may be obtained within the 14 days prior to study product administration, except for a pregnancy test, which must be performed on urine or blood specimens within 48 hours prior to study product administration with negative results received prior to study product administration.

³ Solicited AE assessments are performed daily for at least 3 full days following study product administration. CRS staff will review and reconcile the diary with the participant and then report Solicited AEs. Participant diary reconciliation may happen as the data is available (see the HVTN 140/HPTN 101 SSP). For Part B participants' second infusion solicited AE data collection: remote documentation of the participant diary may occur after the solicited AE assessment period and the next clinic visit (Visit 9), ideally within 2 weeks post-infusion (see the HVTN 140/HPTN 101 SSP).

⁴ Includes transmission risk reduction counseling for HIV-infected participants.

⁵ Contraception status assessment is required only for participants who were assigned female sex at birth and who are capable of becoming pregnant.

⁶ Not applicable to HIV-infected participants.

⁷ Includes pretest counseling and HIV testing. A subsequent follow-up contact is conducted to provide post-test counseling and to report results to participant. Not applicable for participants diagnosed with HIV infection.

⁸ For specimen collection requirements, see [Appendix G](#).

Appendix J HVTN low risk guidelines for the US

The following are intended as guidelines for the investigator to help identify potential vaccine trial participants at “low risk” for HIV infection. These guidelines are based on behaviors within the last 6-12 months prior to enrollment; however, it may be appropriate to consider a person’s behavior over a longer period of time than specified to assess the person’s likelihood of maintaining low risk behavior. *Some volunteers may not be appropriate for enrollment even if they meet these guidelines.* These guidelines should be supplemented and interpreted with local epidemiologic information about HIV prevalence in your area and community networks. The investigator may review the risk level of any volunteer with the site PI and/or the Protocol Safety Review Team.

A volunteer may be appropriate for inclusion if he/she/they meets these guidelines:

A. For US volunteers NOT on stable Pre-exposure prophylaxis (PrEP)

1. SEXUAL BEHAVIORS

In the **last 12 months** did not:

- Have oral, vaginal or anal intercourse with an HIV-infected partner, or a partner who uses injection drugs
- Give or receive money, drugs, gifts or services in exchange for oral, vaginal or anal sex

AND

In the **last 6 months** has abstained from penile/anal or penile/vaginal intercourse, OR

In the **last 6 months**:

- Had 4 or fewer partners of the opposite birth sex for vaginal and/or anal intercourse, OR

Is an MSM (person born male with partner(s) born male) who, in the **last 12 months**:

- Had 2 or fewer MSM partners for anal intercourse and had no unprotected anal sex with MSM, OR
- Had unprotected anal intercourse with only 1 MSM partner, within a monogamous relationship lasting at least 12 months (during which neither partner had any other partners). If the monogamous relationship ended, the volunteer may then have had protected anal intercourse with 1 other MSM partner (total 2 or fewer partners in the last 12 months).

Is a transgender person, regardless of the point on the transition spectrum, having sex with men (born male) and/or other transgender persons, who in the **last 12 months**:

- Had 2 or fewer partners for anal or vaginal intercourse, and had no unprotected anal or vaginal sex, OR
- Had unprotected anal or vaginal intercourse sex with 1 partner only within a monogamous relationship lasting at least 12 months (during which neither partner had any other partners). If the monogamous relationship ended, may

then have had protected anal or vaginal sex with 1 other partner (total 2 or fewer partners in the last 12 months).

AND

Uses or intends to use condoms in situations which may include penile/anal or penile/vaginal intercourse with new partners of unknown HIV status, occasional partners, partners outside a primary relationship, and/or partners known to have other partners.

2. NON-SEXUAL BEHAVIORS

In the **last 12 months** did not:

- Inject drugs or other substances without a prescription
- Use cocaine, methamphetamine, or excessive alcohol, which in the investigator's judgment, rendered the participant at greater than low risk for acquiring HIV infection.
The investigator's judgment should consider local epidemiologic information about HIV prevalence in the area and community networks.

A volunteer is NOT appropriate for inclusion if he/she:

Acquired an STI (ie, new infection) in the **last 12 months**:

- Syphilis
- Gonorrhea
- Non-gonococcal urethritis
- Herpes Simplex Virus type 2 (HSV2)
- Chlamydia
- Pelvic inflammatory disease (PID)
- Trichomonas
- Mucopurulent cervicitis
- Epididymitis
- Proctitis
- Lymphogranuloma venereum
- Chancroid
- Hepatitis B

B. For US volunteers on Pre-exposure prophylaxis (PrEP)

1. PrEP ASSESSMENT

- Reports equal to or greater than six months of protective PrEP use
- Commits to maintaining protective PrEP use throughout trial
- Participant reports equal to or greater than 70% when asked the following:
“Thinking about the past 4 weeks, what percent of the time were you able to take all your PrEP medications?”

2. SEXUAL BEHAVIORS

Persons stably taking PrEP as described above for 6 months or longer are considered low risk of HIV infection, regardless of any sexual behavior that might otherwise be associated with high risk of HIV exposure.

2. NON-SEXUAL BEHAVIORS

In the **last 12 months** did not:

- Inject drugs or other substances without a prescription
- Use cocaine, methamphetamine, or excessive alcohol, which in the investigator's judgment, rendered the participant at greater than low risk for acquiring HIV infection.

The investigator's judgment should consider local epidemiologic information about HIV prevalence in the area and community networks.

Appendix K HVTN low risk guidelines for Southern Africa

The following are intended as guidelines for the investigator to help identify potential vaccine trial participants at “low risk” for HIV infection. These guidelines are based on behaviors within the last 12 months prior to enrollment; however, it may be appropriate to consider a person’s behavior over a longer period of time than specified to assess the person’s likelihood of maintaining low risk behavior. Some volunteers may not be appropriate for enrollment even if they meet these guidelines. These guidelines should be supplemented and interpreted with local epidemiologic information about HIV prevalence in your area and community networks. The investigator may review the risk level of any volunteer with the site PI and/or the Protocol Safety Review Team.

Assessment of sexual behaviors

Consider whether a volunteer would be appropriate for inclusion if, within 12 months prior to enrollment, the person:

- Abstained from penile/vaginal and penile/anal intercourse, or
- Was in a mutually monogamous relationship with a partner with a known HIV-uninfected status, or
- Had one partner believed to be HIV-uninfected with whom he/she regularly used condoms for penile/vaginal and penile/anal intercourse.

Exclude a volunteer if:

Within the 12 months prior to enrollment: a history of newly acquired syphilis, gonorrhea, chlamydia, trichomoniasis, active HSV lesions, chancroid, pelvic inflammatory disease (PID), genital sores or ulcers, cervicitis, genital warts of the labia minora, vagina, or cervix, or any other symptomatic genital warts.

